September 26th 2021

Study Protocol and Statistical Analysis Plan

ClinicalTrials.gov Identifier: NCT04243421

Marginal Bone and Soft Tissue Alterations After Use of OsseoSpeed EV Profile Implants

Aim

Evaluation of the marginal bone and soft tissue alterations after the OsseoSpeed™ EV Profile implants placement in anterior maxilla.

Study design

A case series study. Each patient will provide only one site with sloped ridge for implantation. The trial will have a duration of 1 year.

The principles outlined in the Declaration of Helsinki on clinical research involving human subjects will be adhered to a written informed consent which will be obtained for each patient.

Inclusion criteria

- lack of tooth in position of central incisors, canines and premolars
- minimum age – 18 years

The definitive inclusion of the site will be made at surgery after final osteotomy - if the site demonstrates a lingual-buccal bone height discrepancy of 1.5-2.0 mm.

Exclusion criteria

- Smoking
- Uncontrolled diabetes
- Pregnancy or lactation
- Poor oral hygiene

Number of patients to be included

It is planned to include 30 patients in to the study.

Outcome measures

Implant survival: the reason for implant loss will be recorded.

Complications and adverse events: any complication (flap dehiscence, suppuration, etc.) and adverse events will be recorded and reported by study group by the blinded assessors.

Pink esthetic score (1) – at the temporary crown delivery, at final crown delivery, 6 months post final crown delivery

Papilla index (2) - at the temporary crown delivery, at final crown delivery, 6 months post final crown delivery

Changes in radiographic marginal bone levels and width at buccal and palatal aspects: differences between baseline (the day of surgery) and 1-year measurements on CBCT will be made.

Materials

- Implant OsseoSpeed™ EV Profile \varnothing 4.2 mm
- cover screw
- healing abutment
- temporary abutment
- temporary crown
- impression coping
- implant replica
- Atlantis abutment
- definitive full ceramic crown
- Sutures: non-resorbable 5/0 or 6.0 Ethilon (Ethicon Johnson & Johnson Company, New Brunswick, NJ, USA)

Clinical procedures

Screening visit

Potentially eligible patients are screened to establish their eligibility for the study.

Prior to enrollment, all patients will be asked to sign an informed consent form to document that they understand the scope of the study (including procedures, follow-up evaluations, and any potential risks involved), will be allowed to ask questions pertaining to this study, and will be informed of treatment alternatives. The study is open to qualifying patients without regard to sex or race.

Once identified one or more eligible sites, only one site will be included and treated in the study for each patient: the site demonstrating a lingual-buccal bone height discrepancy of 2.0-3.0 mm visible in CBCT. Preoperative CBCT have to be taken to screen the patient as potentially eligible for being included in the trial.

The definitive inclusion of the site will be made at surgery stage, after final osteotomy – if there will be a lingual-buccal bone height discrepancy of 1.5-2.0 mm measured with a periodontal probe PCP-15 (Hu-Friedy, Leimen, Germany).

Prophylactic procedures: 1 g of Amoxicillin will be taken twice a day starting one hour before the surgical intervention up to the fifth day after surgery. Patients allergic to penicillin will be prescribed 600 mg Clindamycin to be taken twice a day starting one hour before the surgical

intervention up to the fifth day after surgery. Patients will rinse with chlorhexidine mouthwash 0.2% for 1 minute prior to the intervention.

Intraoral facial digital photographs will be made of each potentially eligible site to document the condition of state of soft tissue health. Baseline CBCT have to be taken immediately after surgery.

Surgical procedures

Local anaesthesia – Articain (Ubistesin forte, 3M ESPE, Germany).

Flap will be designed following the crestal and releasing incisions (if necessary). All granulation tissue will be removed and the roots of neighboring teeth will be carefully debrided with hand and/or mechanical instruments. Bone re-contouring is not allowed.

After having completed the cleaning, the surgeon will perform the osteotomy. After the use of the final drill ≈ 3.2 the surgeon will take the measurement of the buccal and palatal/lingual walls height.

If wall discrepancy is 1.5-2mm the site will be included in the study.

Clinical photographs of probe into the osteotomy have to be taken.

The osteotomy will be prepared with the conical drill therefore the implant will be placed in special manner - it's sloped part is located at the buccal osteotomy preparation. The buccal rim of the implant is positioned at the crestal bone level, the palatal rim may be situated either at the level of the bone crest or 0.5 mm below.

The flap will be sutured with 5/0 or 6/0 non-absorbable Ethilon sutures using the mattress and single interrupted sutures. Clinical photographs of the treated site after flap suturing have to be taken.

Post-surgical instructions and follow-up

- Ibuprofen 400 mg 2-4 times per day will be prescribed in case of pain. In case of gastric problems it will be replaced by Paracetamol 1 g (max 4 g per day).
- Patient will be reminded to go on with the antibiotic prophylactic therapy as previously described.
- Chlorhexidine mouthwash 0.12% for 1 minute twice a day for 3 weeks will be provided.
- Suture removal after 2 weeks.

Check-ups and maintenance

Appointments will be scheduled at weeks 1, 2, 4, and 6. Clinical photographs will be taken. At these time points presence of suppuration and flap dehiscence will be recorded dichotomously as presence/absence.

Uncovering procedure will be scheduled at 8 weeks post-op. After crestal incision and gentle flap elevation the height of denudated buccal implant surface (if present) will be measured using a periodontal probe. Then the hilling abutment will be screwed in and single interrupted sutures

will be placed with the use 5/0 or 6/0 non-absorbable Ethilon sutures (if necessary). Suture removal is planned 7 days after procedure. Clinical photographs will be taken.

Temporary crown will be delivered 3 months post implant placement. Clinical examination (PES, PI) will be performed. Clinical photographs will be taken. Control CBCT will be taken.

Final prosthetic reconstruction will be delivered 6 months post-op. Clinical examination (PES, PI) will be performed. Clinical photographs will be taken.

1 year evaluation

Clinical examination (PES, PI) will be performed.

Clinical photographs of the study site have to be taken.

Control CBCT will be taken.

In case of any complication observed during any of the scheduled visit or during an emergency visit, intraoral radiographs and clinical photographs have to be taken and the CRF should be filled in.

Summary of the procedures and follow-up

| | |
|---------|---|
| Day 0 | Antibiotic coverage, preoperative clinical photographs, flap, intrasurgical measurements with definitive inclusion, treatment, post-operative photographs, CBCT |
| Week 1 | Check: suppuration, dehiscence |
| Week 2 | Check: suture removal, suppuration, dehiscence, photographs |
| Week 4 | Check: suppuration, dehiscence, photographs |
| Week 6 | Check: suppuration, dehiscence, photographs |
| Week 8 | Uncovering procedure, intrasurgical measurements, healing abutment installation, photographs |
| Month 3 | Temporary prosthetic reconstruction delivery, PES, PI, photographs, CBCT |
| Month 6 | Definitive prosthetic reconstruction delivery, PES, PI, photographs |
| 1 year | PES, PI, photographs, CBCT. |

Drop-outs

All drop-outs should be reported and the reason for dropping out should be investigated and reported per study group. No included patient can be excluded, for any reasons, by the clinical investigators.

Statistical analysis

The variables will be described by the parameters of descriptive statistics, i.e. arithmetic mean with 95% confidence interval, standard deviation, median, lower and upper quartile, as well as the minimum and maximum value.

The normality of the distribution will be tested with the Shapiro-Wilk test.

For the comparisons of 2 groups, the Student's t-test for related variables or Wilcoxon's test will be used (depending on whether the assumption of normal distribution is met).

Related variables ANOVA or Friedman's test along with Dunn's multiple comparison test with Bonferroni correction will be used to compare the 3 groups (depending on whether the assumption of normal distribution is met). Additionally, the trend analysis will be performed with the Page test or the linear trend test.

The results were considered statistically significant at $p < 0.05$.

PQStat version 1.8.0.392 will be used for statistical analyzes.

Administrative procedures and data management

Clinical record forms (CRFs) should be filled in at the time of data collection. Complete CRFs, and disks containing the digitized clinical photographs and radiographs should be attached to the study folder of each patient.

All data requested for this study will be collected using paper CRFs. The CRFs will be stored in a secure locked place to which only the principle investigator and the responsible for data collection will have access to. Patient identity will be protected and known only to the study participants listed in the present protocol.

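### Do the CBCT screening window (2.0-3.0 mm) and the probe inclusion window (1.5-2.0 mm) conflict, and does the trial need a changed plan because of it?

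*Combined protocol and SAP*

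**What the plan says.** Eligibility is decided in two steps.

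- **Screening.** The Screening visit section gives the purpose of the first scan: "Preoperative CBCT have to be taken to screen the patient as potentially eligible for being included in the trial". One site per patient is chosen, namely "the site demonstrating a lingual-buccal bone height discrepancy of 2.0-3.0 mm visible in CBCT".
- **Definitive inclusion.** The same section makes the final decision at surgery, "if there will be a lingual-buccal bone height discrepancy of 1.5-2.0 mm measured with a periodontal probe PCP-15". The Inclusion criteria section agrees ("if the site demonstrates a lingual-buccal bone height discrepancy of 1.5-2.0 mm"), and the Surgical procedures section gives the same range a third time.

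The Surgical procedures section places the measurement after the final drill, given as about 3.2 with no unit, and does not permit re-contouring of the bone. It allows some tolerance in implant position: "the palatal rim may be situated either at the level of the bone crest or 0.5 mm below".

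On numbers, the protocol says "It is planned to include 30 patients in to the study" and gives no figure for sites to be screened or opened. On losses, the Drop-outs section says "All drop-outs should be reported and the reason for dropping out should be investigated" and bars investigators from excluding anyone already included. No section asks for a log of sites screened, opened and not included.

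**The concern.** Both windows carry the same name, a lingual-buccal difference in bone height, yet they touch only at 2.0 mm. If the quantity did not change between scan and surgery, only a site at exactly 2.0 mm could pass both steps. A site read as 1.7 mm on CBCT would lie inside the surgical range but would fail the screen. Since re-contouring is not allowed, that cannot be the intended source of a reduction, and the protocol offers no other.

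Two things would be at stake. The first is feasibility: if few screened sites qualify, many flaps and osteotomies would be needed to reach 30 inclusions. The second is description of the sample: with selection completed during surgery and no count requested, a reader might not learn what share of screened sites the 30 represent.

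**Working it through.** The plan gives no yield or screening number, so there is no figure of its own to reproduce. The check asks whether the windows can work together and whether anything downstream depends on the answer.

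**Inputs from the documents.** CBCT reading D in 2.0-3.0 mm; probe reading S in 1.5-2.0 mm; final drill about 3.2; 30 inclusions.

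**Assumptions, not in the documents.** D spread evenly over 2.0-3.0 mm; the drill figure in mm; the form of the link between D and S; probe rounding where stated.

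**Step 1: direct overlap.** From max(2.0, 1.5) = 2.0 to min(3.0, 2.0) = 2.0, a width of 0 mm.

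**Step 2: reduction needed to qualify**, D − 2.0 to D − 1.5.

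- D = 2.0: 0 to 0.5 mm.
- D = 2.5: 0.5 to 1.0 mm.
- D = 3.0: 1.0 to 1.5 mm.

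The first and last ranges do not meet, so with exact readings no single fixed reduction admits every screened site. The ratios S/D also fail to meet: 0.75-1.00 at D = 2.0 and 0.50-0.67 at D = 3.0. A link that varies by site can admit all of them. For example, S = 0.5D + 0.5 sends 2.0 to 1.5 and 3.0 to 2.0.

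**Step 3: share qualifying under one fixed reduction r.** With exact readings, D must lie in 1.5 + r to 2.0 + r. If the probe is read to the nearest 0.5 mm, true values of 1.25-2.25 are accepted, so D must lie in 1.25 + r to 2.25 + r.

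| r (mm) | Exact | Rounded to 0.5 mm |
|---|---|---|
| 0 | 0% | 25% |
| 0.5 | 50% | 75% |
| 0.75 | 50% | 100% |
| 1.0 | 50% | 75% |

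**Step 4: share qualifying under a straight ridge slope.** If D is read across a ridge of width W and S across the drill, then S = D × 3.2/W. A site qualifies when D lies in 1.5W/3.2 to 2.0W/3.2, or 1.25W/3.2 to 2.25W/3.2 with rounding. At W = 4.8 mm the exact range is 2.25 to 3.0, which is 75% of the screening window.

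| W (mm) | Exact | Rounded to 0.5 mm |
|---|---|---|
| 3.2 | 0% | 25% |
| 4.0 | 50% | 81% |
| 4.8 | 75% | 100% |
| 5.0 | 66% | 100% |
| 6.0 | 19% | 66% |

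**Step 5: sites opened for 30 inclusions**, 30/p, where p is the share qualifying. At 100%, 30; at 75%, 40; at 50%, 60; at 25%, 120. The choice among these comes entirely from the assumed link.

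**Step 6: what depends on the screening window.** The Outcome measures section takes baseline for the radiographic changes on the day of surgery, and the Screening visit section has that baseline CBCT made immediately after surgery. The preoperative scan is therefore not the baseline for any outcome. The Statistical analysis section describes the variables and makes paired or repeated comparisons within included patients. No summary or test takes the preoperative discrepancy as an input.

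**The case for a change.** The strongest case for a change is that this is a single-arm case series, where readers lean heavily on knowing how the sample was chosen, and here the deciding step happens with the flap raised. A site that misses the surgical range is neither a drop-out nor a protocol violation, so neither reporting rule clearly captures it. The summary of procedures starts at Day 0 and has no screening row. A sentence on the expected link and a line in a log would cost almost nothing.

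The factual part stands: the link is not stated and the count is not requested. Its consequence is limited.

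- A first-stage screen need not pass every site. The surgical check is there because some will fail, so the lack of one fixed reduction covering the whole range is not a fault.
- The surgical criterion tells a reader exactly which sites were studied, whatever the yield.
- Some source records will exist. The protocol calls for photographs of each potentially eligible site and of the probe in the osteotomy, and lists intrasurgical measurements on Day 0. These are not a count, but they could help the authors assemble one.
- A request for patient-flow numbers could be made of any protocol without a screening log. It does not arise from these two windows.

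The 0.5 mm width of the surgical window equals the 0 to 0.5 mm palatal tolerance, which might suggest a geometric reason for it. The protocol does not say so, and nothing here rests on it.

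**Conclusion.** The concern calls for no change. The windows differ because they belong to different stages and measurements. They can work together under several simple assumptions, with 50% to 100% of screened sites qualifying at ridge widths of 4.0 to 5.0 mm in the straight-slope illustration. Other assumptions give far less, and the full range of 0% to 100% shows only that the documents do not settle the yield. They do not point to the unfavourable end, so the figure of 120 opened sites is an illustration and not a demonstrated risk.

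Followed exactly as written, the plan produces a clearly defined sample of 30, and its within-patient results do not depend on the screening window. Stating the expected CBCT-to-probe relation and giving the numbers screened, opened and not included would be good reporting, and the investigators can supply both in the publication. Neither would alter an estimate, interval or test. Which windows to use remains a matter for the sponsor and investigators.

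### Three-visit comparisons: no pairwise test for the ANOVA branch, an avoidable Bonferroni penalty, and an unstated tie rule for Dunn's test that can hide visit-to-visit changes in PES and papilla index

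*Combined protocol and SAP*

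**What the plan says.** The Outcome measures section schedules both soft-tissue scores at three visits: "Pink esthetic score (1) – at the temporary crown delivery, at final crown delivery, 6 months post final crown delivery" and "Papilla index (2) - at the temporary crown delivery, at final crown delivery, 6 months post final crown delivery". The follow-up schedule places these at month 3, month 6 and 1 year. CBCT is scheduled on day 0, at month 3 and at 1 year, although the outcome definition compares only baseline with 1 year.

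The Statistical analysis section chooses between parametric and rank methods by a normality test ("The normality of the distribution will be tested with the Shapiro-Wilk test"). For three related measurements it says: "Related variables ANOVA or Friedman's test along with Dunn's multiple comparison test with Bonferroni correction will be used to compare the 3 groups". It adds: "Additionally, the trend analysis will be performed with the Page test or the linear trend test". Paired tests appear only for two-measurement comparisons: "For the comparisons of 2 groups, the Student's t-test for related variables or Wilcoxon's test will be used". The significance level is p < 0.05. The section does not mention tie handling, and it does not say whether pairs are tested only after a significant overall test. The sample size ("It is planned to include 30 patients in to the study") comes with no power calculation.

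**The concern.** The pairwise tests are what would say between which visits the soft tissue changed, and soft-tissue alteration is half of the stated aim. Three features of the sentence weaken them.

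- **ANOVA branch.** Dunn's is a rank procedure and reads as the companion of Friedman's test. If ANOVA is used, no pairwise contrast is specified, and the analyst would have to choose one after seeing the data.
- **Bonferroni.** Holm controls the same familywise error and rejects at least as often, so Bonferroni gives up power for nothing.
- **Ties.** PES and papilla index are scores, and many patients may hold the same score at two or three visits. Dunn's z in its textbook form uses a variance that assumes no ties within a patient. With many ties that variance is too large and the test too conservative. The plan does not say which form will be used.

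At stake is a result in which the overall test is clearly significant but no pair of visits is.

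**Working it through.** The plan gives no power figure, effect size or SD, so there is no stated figure to reproduce.

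**Inputs from the document.** n = 30; k = 3 visits; alpha 0.05 (two-sided assumed, since sidedness is not stated); 3 pairs, so 0.05/3 = 0.0167 per pair and critical z = 2.394.

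**Dunn without tie correction.** z = (rank-sum difference) / sqrt(n·k·(k+1)/6).

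- Denominator: sqrt(30·3·4/6) = sqrt(60) = 7.75.
- Rank-sum difference needed: 2.394 × 7.75 = 18.54.
- Suppose c patients gain one step between the first and last visit, the middle visit is tied with one end, and the other 30 − c patients do not change. Each improver's ranks are (1.5, 1.5, 3) or (1, 2.5, 2.5), which adds 1.5 to the first-to-last difference. Unchanged patients add 0.
- c = 12: 18.0/7.75 gives z = 2.32, p = 0.0201, × 3 = 0.060 (not significant).
- c = 13: 19.5/7.75 gives z = 2.52, adjusted p = 0.035 (significant).

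**The same 12 patients under other tests.**

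- Tie-corrected Friedman: Q = 18, p = 0.0001 if the middle visit splits 6/6; Q = 24, p = 0.000006 if all the change comes at the last visit.
- Exact signed-rank: 2/2^12 = 0.0005; × 3 = 0.0015.
- Tie-corrected Dunn: the variance is multiplied by A = sum of (rank − 2)² / (2n). Each improver contributes 1 + 0.25 + 0.25 = 1.5, so A = 12 × 1.5/60 = 0.3. Then z = 18.0/sqrt(60 × 0.3) = 4.24, adjusted p = 0.00007.

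The smallest number of one-way improvers that is significant at 0.0167 is therefore 13 for uncorrected Dunn, 7 for exact signed-rank (2/2^7 = 0.0156) and 4 for tie-corrected Dunn (z = 6.0/sqrt(60 × 0.1) = 2.45).

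**Simulated power, n = 30, all three methods with Bonferroni.** Score ranges, SDs, shifts and correlations are assumptions; none is in the document.

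*4-level score, total shift 0.5 latent SD, within-patient correlation 0.5 to 0.8, first versus last visit:* uncorrected Dunn about 19% to 39%; tie-corrected Dunn or Wilcoxon about 42% to 77%.

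*Rounded scores, linear change, first versus last visit.* PES-like: 0–10, between- and within-patient SD 1.3 and 0.5. Papilla-like: 0–4, SDs 0.6 and 0.35.

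| Score, shift | Dunn, uncorrected | Dunn, tie-corrected | Wilcoxon |
|---|---|---|---|
| PES-like, 0.3 | 0.09 | 0.31 | 0.30 |
| PES-like, 0.5 | 0.46 | 0.77 | 0.76 |
| PES-like, 0.7 | 0.88 | 0.97 | 0.97 |
| Papilla-like, 0.2 | 0.02 | 0.22 | 0.19 |
| Papilla-like, 0.4 | 0.35 | 0.80 | 0.77 |
| Papilla-like, 0.6 | 0.90 | 0.995 | 0.99 |

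In these settings 86% to 98% of patients had at least one tie. With no true change, the familywise error of uncorrected Dunn was 0 to 0.7%, against a nominal 5%.

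**Without ties.** The two Dunn forms then coincide. For continuous data with a linear shift of 0.7 within-patient SD, power was 0.42 for Dunn, 0.53 for Wilcoxon and 0.56 for paired t, all with Bonferroni.

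**Holm in place of Bonferroni.** The ordered p-values are compared with 0.05/3, 0.05/2 and 0.05 rather than 0.05/3 each time. Holm-adjusted paired t or tie-aware signed-rank tests were level with or above Dunn-Bonferroni in almost all runs and never more than about 3 points below. Gains were 3 to 15 points on adjacent visits or step changes, with familywise error of 3% to 5%.

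**The case against.** Four objections have force.

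- **The large loss depends on a formula the plan does not state.** The section names Dunn's test and a software version, not a variance. In the 12-patient example tie-corrected Dunn gives a smaller p-value than the signed-rank test. This stands: a reader might infer that Dunn's test as such forfeits the power and must be deleted, but on tied scores its corrected form matches Bonferroni-adjusted Wilcoxon.
- **Adjusted and unadjusted tests must not be mixed.** Setting Bonferroni-adjusted Dunn against signed-rank tests run at 0.05 after a significant overall test gives a wider gap (13 improvers against 6), but part of that gap is the dropped adjustment. The table above therefore uses Bonferroni throughout. The plan states no gate on the overall test, so some adjustment is needed as written.
- **The ANOVA branch may rarely be used for these scores.** In simulated coarse scores the Shapiro-Wilk test rejected normality for at least one visit in 96% to 100% of trials. The missing contrast would matter more for CBCT, if its three scans are compared. A reader might also infer that Dunn is meant to follow ANOVA; the word order does not support that.
- **Overall change would not go unreported.** A reader might conclude that the paper would show no soft-tissue change. The trend test and the descriptive summaries with confidence intervals count against that. A one-sided Page test at 0.05 had power 0.84 to 0.94 (PES-like, shift 0.5) and 0.79 to 0.95 (papilla-like, shift 0.4), the lower figure without tie correction. It does not say between which visits the change occurred.

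**Conclusion.** The point holds as an under-specification together with an avoidable loss of power. Two parts need no assumption about the data: the ANOVA branch lacks a pairwise contrast, and Holm would reject at least as much as Bonferroni with the same error control.

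The third part is conditional. If the Dunn variance is not tie-corrected, changes between specific visits can be missed, with a loss of roughly 20 to 45 points at small to moderate shifts and about 10 points at the largest shifts examined. If it is tie-corrected, most of that loss disappears on coarse scores, and the remaining gain comes mainly from replacing Bonferroni.

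The 12-versus-13 boundary is exact for the pattern described. The power figures rest on assumed score levels, shifts, SDs and correlations. The documents do not support saying that real changes will be missed: large changes were detected about 90% of the time even without tie correction.

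**What to change.** Replace the pairwise part of the sentence with: *The three visit pairs will be compared with paired t-tests in the ANOVA branch and with Wilcoxon signed-rank tests (exact or tie-corrected) in the Friedman branch, two-sided, with Holm adjustment over the three pairs.* If Dunn's test is kept for the Friedman branch, specify the tie-corrected variance and Holm.

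Testing the pairs unadjusted at 0.05 only after a significant overall test is also acceptable with exactly three visits, because any two pairwise equalities imply the third. It is an option, not a requirement, and the gate would have to be written down.

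The cost is one sentence. Both paired tests are already named in the plan and no new data are needed. The downside is that the signed-rank test uses the size of score differences, which is debatable for an ordinal index, and it can be up to about 3 points less powerful than tie-corrected Dunn in some tied-score settings.

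### On the rank branch, with three visits, Page's trend test is the same statistic as Dunn's first-versus-last comparison, so the month-3 to 1-year change is judged at about 0.0167 and again at 0.05

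*Combined protocol and SAP*

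**What the plan says.** Outcome measures schedules the pink esthetic score and the papilla index "at the temporary crown delivery, at final crown delivery, 6 months post final crown delivery". Check-ups and maintenance dates the first two of these: "Temporary crown will be delivered 3 months post implant placement" and "Final prosthetic reconstruction will be delivered 6 months post-op". The three scorings therefore fall at months 3, 6 and 12. The planned number is given as "It is planned to include 30 patients", with one site each.

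For three related measurements, Statistical analysis states: "Related variables ANOVA or Friedman's test along with Dunn's multiple comparison test with Bonferroni correction will be used to compare the 3 groups". The next sentence adds the trend test: "Additionally, the trend analysis will be performed with the Page test or the linear trend test". One general threshold follows: "The results were considered statistically significant at" p < 0.05.

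The Bonferroni correction is attached to Dunn's test only. The section does not give the number of pairs, the trend scores, the direction or sidedness of the trend test, the handling of ties, or what to conclude if the trend test and the pairwise test disagree.

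**The concern.** A trend test announced as an addition suggests a further piece of evidence. With three visits, Page's test gives the middle visit no weight and reduces to last visit against first. Dunn's test already makes that comparison under the plan's own correction. The second look has no correction.

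The report could then state a significant trend in PES and, from the same number, no significant change between the first and last visit. Readers would take the trend as independent support, and the authors would have no stated rule for choosing between the two results. In a case series the harm is a misleading sentence in the paper, not a wrong treatment decision.

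**Working it through.** **Inputs.** From the documents: n = 30, k = 3 visits, general threshold 0.05. Inferred: all three pairs are compared, so the Bonferroni level is 0.05/3 = 0.0167. The plan gives no error rate or power for these tests, so there is no figure to reproduce.

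**Identity on the rank branch.** Let R1, R2, R3 be the rank sums at months 3, 6 and 12.
- Without loss of generality R1 + R2 + R3 = 6n, so Page's L = R1 + 2·R2 + 3·R3 = 12n + (R3 − R1).
- Without ties, E(L) = nk(k+1)²/4 = 12n and Var(L) = nk²(k+1)²(k−1)/144 = 2n.
- Page z = (R3 − R1)/√(2n).
- Dunn z, first versus last = [(R3 − R1)/n] / √(k(k+1)/(6n)) = (R3 − R1)/√(2n).

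The two are equal. In 5,000 untied and 5,000 tied simulated data sets, with neither test tie-corrected, they differed by no more than 2 × 10⁻¹⁵. If only one test is tie-corrected, the numerator is shared but the z values differ; one tied example gave 1.68 uncorrected and 2.01 corrected.

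**Where the two rules disagree (n = 30, no ties, two-sided).** The critical |z| is 1.960 at 0.05 and 2.394 at 0.0167. Multiplied by √60, these are rank-sum differences of 15.18 and 18.54.

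| R3 − R1 | z | Page p | Bonferroni p (3 × p) |
|---|---|---|---|
| 15 | 1.936 | 0.053 | 0.158 |
| 16 | 2.066 | 0.039 | 0.117 |
| 17 | 2.195 | 0.028 | 0.085 |
| 18 | 2.324 | 0.020 | 0.060 |
| 19 | 2.453 | 0.014 | 0.043 |

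Differences of 16, 17 and 18 give opposite verdicts. For example, rank sums 52, 60, 68 give Friedman Q = (52² + 60² + 68²)/30 − 360 = 4.27, p = 0.118. First versus last has Bonferroni p = 0.117, yet the trend has p = 0.039.

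**Chance of any claim with no true change (simulated, n = 30).**
- No ties: the three Dunn-Bonferroni comparisons alone, about 4.3%; with two-sided Page at 0.05 added, about 6.9% (runs ranged from 6.7% to 6.9%). If Page were one-sided at 0.05, about 8.5%.
- Ties, with 4 or 11 score levels and a visit correlation of 0.5 assumed: about 7% with Page added if both tests are tie-corrected. If neither is, about 2% (4 levels) and 4.5% (11 levels), both below 5%.

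**Chance of opposite verdicts on first versus last (rank tests, no ties).** It is 2.8% with no true change, and 11%, 15%, 16% and 14% at assumed changes of 0.3, 0.4, 0.5 and 0.6 SD of the change.

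**ANOVA branch.** Equally spaced scores give the contrast (−1, 0, 1), which is the last-minus-first mean difference; its t equals the pairwise t when both use the same error term. Scores by actual month (3, 6, 12; mean 7) give (−4, −1, 5). The correlation of that contrast with (−1, 0, 1) is (4 + 5)/√(42 × 2) = 9/9.165 = 0.98 under compound symmetry, which is close but not the same statistic.

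**The case against.** Four arguments stand against making more of this.

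1. A reader might infer that the trend test always duplicates the first-versus-last comparison. The documents do not support that. The plan also allows a linear trend test, gives no scores, and has unequally spaced visits. On that branch the overlap is exact only with equally spaced scores and a common error term.
2. A reader might attach an error rate to the ANOVA branch. The plan names no Bonferroni-corrected paired t-test. If Dunn's test belongs to Friedman only, the ANOVA branch has no corrected pair to contradict. If Dunn's rank test follows ANOVA, it is a different statistic from a contrast of means. Any such rate would test a procedure that the plan does not name.
3. A reader might conclude that the overall error rate must exceed 5%. These outcomes are scores, so ties are likely, and the result depends on how the named software treats them. If neither test is tie-corrected, the rate stays below 5%.
4. The study is a case series that names no primary test and makes no familywise error claim. The trend test is plainly an addition. The planned descriptive statistics and the other two Dunn comparisons would show where month 6 lies.

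All four stand, and they limit the scope and size of the point. They do not remove it: on the rank branch, the plan's own two rules can give contrary answers to one number, and calling the trend test supplementary does not say which answer to report.

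**Conclusion.** The point holds for PES and papilla index on the Friedman, Dunn and Page branch, and it is minor. The month-3 to 1-year change is judged at about 0.0167 and again at 0.05. The identity is exact if both tests or neither are tie-corrected.

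The size without ties is a band of three rank-sum differences with opposite verdicts, and a rise of about 2.6 percentage points (6.9 − 4.3) in the null chance of any claim. This rests on three pairs in the Bonferroni set and a two-sided Page test, neither of which the plan states. The figures at non-zero changes rest on assumed effect sizes, and the tied figures on assumed score levels and visit correlation. For the ANOVA branch, the documents support only the statement that the overlap is exact or near-exact depending on the scores and error term.

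**What to change.** Drop the Page or linear trend test for the three-visit outcomes and report the first-to-last change from the Bonferroni-corrected comparison. This takes one sentence, needs no new data and loses no information on the rank branch. The cost is the looser threshold for that pair: the chance of a significant result falls from about 61% to 45% at an assumed change of 0.5 SD, and from 43% to 28% at 0.4 SD (rank tests).

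If month 3 to 1 year is the change of real interest, the alternative is to name it as the single planned comparison at two-sided 0.05 and report the other two pairs descriptively only. This keeps the power for that change and gives up formal claims about the other two pairs. Also testing those two at 0.025 each would raise the null chance of any claim to about 8%, worse than the plan as written.

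If the data had already been seen when the change is made, label it post hoc.
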